6.10 Randomization

Treatment kits will be sequentially assigned to subjects. Within each kit there will be test articles (IP, vehicle gel, aqueous gel) to be applied to the chest and back. The subject and the Investigator will be blinded to the pre-defined randomization assignments of IP and vehicle gel.

6.11 Treatment Compliance

Subjects will receive either a single treatment application on one day, or once daily application of the test articles for 5 consecutive days at the investigative site by designated study personnel. This will allow for well documented compliance as the Investigator or designee will record the time, date, and other details of test article administration.

7 DATA ANALYSIS AND STATISTICAL CONSIDERATIONS

7.1 General Statistical Considerations

All statistical processing will be performed using Statistical Analysis System (SAS[®]) unless otherwise stated. No interim analyses are planned. Except where noted, all statistical tests will be two-sided and will be performed at the 0.05 level of significance. P-values will be provided primarily for exploratory purposes.

Descriptive statistics will be used to provide an overview of the efficacy and safety results. For categorical parameters, the number and percentage of subjects in each category will be presented. For continuous parameters, descriptive statistics will include n (number of subjects), mean, and standard deviation, median, minimum, and maximum. Appropriate inferential statistics will be used for the primary and secondary efficacy variables in an exploratory manner. Linear interpolation of efficacy variables will be performed using observed data that precedes and follows the off-schedule visit, if present. The last observation will be carried forward if all the data subsequent to the off-schedule value is missing. No adjustments will be made for multiplicity.

The number of subjects in each analysis set will be summarized. Reasons for study withdrawal will be summarized using frequencies and percentages by treatment group. Reported AEs, medical history terms and prior and concomitant procedures and therapies will be classified on the basis of

7.3 Analysis of Safety Data for Objectives

7.3.1 Local Tolerability

Signs and symptoms of local tolerability (pain / burning / stinging, pruritus, erythema, edema, and scabbing / crusting) will be summarized with changes from baseline.

7.3.2 Adverse Events

Subjects will be assessed for the occurrence of new and ongoing AEs. Descriptions of AEs will include the dates of onset and resolution (if resolved), maximum severity, seriousness, action taken regarding the investigational product, corrective treatment, outcome, and Investigator's assessment of causality. All AEs will be recorded and classified using terminology

. All reported treatment-emergent AEs (TEAEs), defined as any AE with an onset on or after the date of first study drug application, will be summarized by treatment group, the number of subjects reporting TEAEs, system organ class, preferred term, severity, and relationship to study drug. When summarizing TEAEs by severity or relationship to study drug, each subject will be counted only once within a system organ class or a preferred term using the event with the greatest severity or causality, respectively, within each category. All reported serious adverse events (SAEs) will be summarized by treatment group, the number of subjects reporting SAEs, system organ class, preferred term, severity, and relationship to study drug.

All information pertaining to AEs noted during the study will be listed by subject and will include a verbatim description of the event as reported by the Investigator, as well as the preferred term, system organ class, start date, stop date (if stopped), seriousness, severity, action taken regarding the study drug, corrective treatment, outcome and relationship to the study drug. In addition, a listing of subjects who prematurely discontinue from the study due to AEs will be provided as well as a listing of subjects who reported an SAE.

7.4 Analysis Populations

All subjects who are randomized and dispensed study drug product will be included in the Intentto-Treat analysis set. All subjects who are randomized, receive at least one (1) confirmed dose of study drug product, and have at least one (1) post-baseline safety assessment will be included in the Safety analysis set.

7.5 Sample Size Determination

Sample size is based on clinical judgement and deemed adequate to successfully demonstrate these goals.

8 ASSESSMENT OF SAFETY

8.1 Safety Evaluations and Criteria

As detailed in section 6.6.2, local tolerability will be evaluated by recording the severity of the signs of TV as well as the signs and symptoms of local tolerability on treated areas involved with TV. In addition, adverse events will be documented.

8.2 Adverse Event

An AE is any untoward medical occurrence in a subject administered a pharmaceutical product, which does not necessarily have a causal relationship with the treatment. An AE can be any unfavorable and unintended sign (e.g., including an abnormal laboratory finding), symptom, or disease temporally associated with the use of the study drug, whether or not it is considered to be study drug related. This includes any newly occurring event or previous condition that has increased in severity or frequency since the administration of study drug (treatment-emergent).

8.3 Serious Adverse Event

A serious adverse event is any AE, occurring at any dose level and regardless of causality that:

- Results in death.
- Is life-threatening: Life-threatening means that the subject was at immediate risk of death from the reaction as it occurred, (i.e. it does not include a reaction which hypothetically might have caused death had it occurred in a more severe form).
- Requires inpatient hospitalization or prolongation of existing hospitalization.
- Results in persistent or significant disability/incapacity.
- Is a congenital anomaly/birth defect.
- Is an important medical event: an important medical event is an event that may not result in death, be life-threatening, or require hospitalization but may be considered an SAE when, based upon appropriate medical judgment, it may jeopardize the subject and may require medical or surgical intervention to prevent one of the outcomes listed in the definitions for SAEs. Examples of such medical events include allergic bronchospasm requiring intensive treatment in an emergency room or at home, blood dyscrasias or convulsions that do not result in inpatient hospitalization, or the development of drug dependency or drug abuse.

A hospitalization for an elective procedure will not be considered a SAE. Any SAE occurring in the study will be reported to the IRB/IEC and Sponsor in compliance with all reporting requirements. Any SAE must be reported to the National Ethics Committee within 24 hours from the time of the investigative site's awareness.

8.4 Unexpected Adverse Event

An unexpected AE is an AE that is not reported in the Investigator's Brochure (IB).

8.5 Relationship of Adverse Events to Study Drug

The following classifications should be used when evaluating the relationship of AEs and SAEs to the investigational drug.

- 1. **None**: No relationship between the experience and the administration of study drug; related to other etiologies such as concomitant medications or subject's clinical state.
- 2. Unlikely: The current state of knowledge indicates that a relationship is unlikely.
- 3. **Possibly**: A reaction that follows a plausible temporal sequence from administration of the study drug and follows a known response pattern to the suspected study drug. The reaction might have been produced by the subject's clinical state or other modes of therapy administered to the subject.
- 4. **Probably**: A reaction that follows a plausible temporal sequence from administration of the study drug and follows a known response pattern to the suspected study drug. The reaction cannot be reasonably explained by the known characteristics of the subject's clinical state or other modes of therapy administered to the subject.
- 5. **Definitely**: A reaction that follows a plausible temporal sequence from administration of the study drug and follows a known response pattern to the suspected study drug and can be confirmed with a positive re-challenge test or supporting laboratory data.

Severity:

- 1. Mild: Awareness of sign or symptom, but easily tolerated
- 2. Moderate: Discomfort enough to cause interference with normal daily activities
- 3. Severe: Inability to perform normal daily activities
- 4. Life-threatening: Immediate risk of death from the reaction as it occurred

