The reason Malassezia spp. grow more actively on the skin of patients that exhibit tinea versicolor is unknown at present but may involve the activation of a tryptophan-dependent metabolic pathway. There are three common classifications of TV, white (hypopigmented), brown (hyperpigmented), and pink (inflamed). Hypopigmentation, or loss of color, is potentially caused by a fungal metabolite altering melanocyte function. Alternatively, there is evidence that Malassezia can also induce enlarged melanosomes in basal melanocytes, causing a brown hyperpigmented type of TV, and it is easiest to see the Malassezia spp. hyphae in this type. Inflammation and dermatitis from the fungus itself or its metabolites is responsible for the pink color of the third type of TV. Inflamed TV and seborrheic dermatitis may co-exist, and all three types of TV can co-exist but are usually considered distinct. TV occurs more often in teenagers and young adults and appears on the back neck, upper chest, shoulders, armpits and upper arms. TV is more likely to occur in hot, humid conditions or in patients with a suppressed immune system. Although it is not considered infectious in the conventional sense, TV sometimes affects more than one member of a family. TV may chronically recur in certain predisposed patients (Theelen et al., 2018). The most common treatment of Malassezia is with antifungal azoles, often ketoconazole. A more effective treatment that targets the root cause of TV is needed due to the increasing incidences of persistent cases and antifungal-resistance in fungi in general (Perlin et al., 2017), including some Malassezia spp. (Peano et al., 2020). In many cases, topical treatment of Malassezia using common azoles is complicated by, not only antifungal resistance, but also side effects, poor compliance, and inconsistent clinical efficacy (Angiolella et al., 2017).

The use of topical live bacterial products to treat skin diseases is a new and rapidly advancing therapeutic approach. To date, at least three live bacterial products have been studied in the clinic. An ammonia oxidizing bacterium has been used in Phase 2 trials to treat acne at a dose of 10⁹ CFUs/ml (Whitlock 2017). In addition, a coagulase-negative Staphylococcus strain at a dose of 107CFUs/ml(Williams & Gallo, 2015) has been used in atopic dermatitis patients, a strain of P. acne has been applied to the face of acne patients at a dose of 108CFUs/ml (NCT03450369), and

[figure not shown]

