6.4.3 Stopping Rules

The sponsor (Medical Director/Chief Medical Officer) will halt the study for a review of the safety data if there are safety concerns noted for any reason and if one or more subjects experience two AE's assessed as a Grade 3 (severe) or higher, of the same type that is considered possibly, probably or definitely related to the IP.

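### All three related grades in 8.5 require an undefined known response pattern, so a well-timed adverse event of a new kind has no causality grade and does not count toward the 6.4.3 halt

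*Combined protocol and SAP*

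**What the plan says.** Section 8.5 gives five causality grades and introduces them as the scale to apply: "The following classifications should be used when evaluating the relationship of AEs and SAEs to the investigational drug".

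- *None*: "No relationship between the experience and the administration of study drug", with the event attributed to other causes.
- *Unlikely*: "The current state of knowledge indicates that a relationship is unlikely".
- *Possibly* and *Probably* share one opening sentence: "A reaction that follows a plausible temporal sequence from administration of the study drug and follows a known response pattern to the suspected study drug". They differ only in whether the subject's condition or other therapy might explain the event.
- *Definitely* has the same timing condition, and the event "follows a known response pattern to the suspected study drug and can be confirmed with a positive re-challenge test or supporting laboratory data".

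Three other sections bear on these grades:

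- Section 6.4.3 has the sponsor halt the study for safety review when one or more subjects have two AEs of Grade 3 or higher, "of the same type that is considered possibly, probably or definitely related to the IP".
- Section 7.3.2 summarises treatment-emergent and serious AEs by relationship to study drug, among other breakdowns.
- Section 9.2, like the Synopsis, provides at the final visit for continued follow-up of study-related AEs.

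Section 8.4 separately defines an unexpected AE as one not reported in the Investigator's Brochure (IB).

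**The concern.** Section 3 puts safety and tolerability first among the purposes of the trial, and section 1.1 introduces the product class with the words "The use of topical live bacterial products to treat skin diseases is a new and rapidly advancing therapeutic approach". In such a trial the most informative AE may be one of a kind not seen before. The scale asks for a pattern that is already known before it allows any grade of relatedness, so it has no place for that event.

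The within-subject design sharpens the point. A reaction confined to one of the two treated sites and returning with each daily application would be good evidence of causation, yet 8.5 offers no related grade if the pattern is new. At stake are the only mandatory halt in the protocol, the way new reactions appear in the safety tables, and possibly their follow-up after the last visit.

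**Working it through.** No figure is stated and no arithmetic applies beyond counting. The check sets the definitions side by side and asks which grade is open to an AE with plausible timing, no known response pattern, and a relationship that has not been excluded.

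| Grade (8.5) | Plausible timing required | Known pattern required | Further condition | Fits this AE? |
|---|---|---|---|---|
| None | no | no | no relationship; other cause | No: a relationship has not been excluded |
| Unlikely | no | no | current knowledge points away from a relationship | No: absence of knowledge is not evidence against |
| Possibly | yes | yes | another explanation may exist | No: pattern condition fails |
| Probably | yes | yes | no reasonable other explanation | No: pattern condition fails |
| Definitely | yes | yes | re-challenge or laboratory confirmation | No: pattern condition fails |

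1. The requirement stands in 3 of 3 related grades. None of the three (0 of 3) can be reached on timing alone.
2. In *Definitely*, confirmation is added to the known pattern and does not replace it. Even a positive re-challenge does not open that grade to a reaction of a new kind.
3. The event fits 0 of 5 grades. This is a gap in the scale. The text does not direct the assessor to any particular grade.
4. Section 6.4.3 counts exactly the three related grades. Its reference to safety concerns for any reason is joined to the count by *and*, so as written it is not a separate trigger. A severe, repeated event without a related grade does not meet the rule.
5. The rule needs two qualifying AEs of the same type. If exactly two occur and one is not graded as related, 2 − 1 = 1 remains and the condition fails. Enrolment is about 3 × 6 + 4 = 22 subjects, of whom about 3 × 6 = 18 receive the probiotic, so one grading decision can settle the matter.
6. In 7.3.2 the event still appears by preferred term and severity and in the listings, but not as related. In 9.2 all AEs are followed during the study, while the sentence on the final visit names only study-related ones.
7. Unexpected under 8.4 means absent from the IB. Section 8.5 does not refer to the IB. The two sets overlap, but neither definition makes them identical.

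**The case against.** A reader might infer more than this: that no unexpected AE can ever be graded as related, so that the category of unexpected and related events is empty by construction. The documents do not support that. An event absent from the IB may still match a pattern known from elsewhere. Section 2.1 names worsening of tinea versicolor, localised infection, cellulitis and systemic infection, and describes the organism as a reported opportunistic pathogen. Section 6.6.2 lists five application-site reactions to be graded. An investigator could reasonably treat any of these as known. Section 1.1 also says that at least three live bacterial products have already been studied in the clinic.

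A reader might also infer that the text forces such events into *None* or *Unlikely*, or that they would escape review. Neither follows. Those two definitions do not fit, so any downgrade would be the assessor's choice. Review outside the causality scale is substantial:

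- Section 6.4.2 allows discontinuation of the study for unusual AEs.
- Section 4.1.1 makes enrolment of each next group depend on there being no safety signals, with no causality filter.
- Section 6.4.1 lets the investigator withdraw a subject for any perceived safety risk.
- Section 8.3 defines SAEs regardless of causality, with reporting to the ethics committee within 24 hours.
- Section 7.3.1 summarises local tolerability without attribution.

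For the halt, the affected set is also narrow: events must be severe, repeated, of one type and without a known pattern.

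All of this stands as a limit on the point, but it does not remove it. Section 6.4.2 is discretionary, safety signals are not defined, and SAE reporting does not reach a severe but non-serious reaction. None of these provisions returns the event to the 6.4.3 count or to the related rows of the tables. Investigators may well grade sensibly in spite of the wording, but they would then be departing from the written definition, and not necessarily all in the same way.

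**Conclusion.** The point holds for AEs with plausible timing and no known response pattern. Such an event has no grade in 8.5 and so falls outside the mandatory halt and the related rows of the safety tables; its follow-up after Day 14 is uncertain. This is a faulty rule and not merely missing detail, because following the text exactly produces the result.

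No share of unexpected AEs should be attached to it. That share depends on the content of the IB, on how assessors read an undefined term, and on how far they depart from the wording, none of which the documents give. The conclusion also assumes that the opening of section 9, including 9.1, which was not available for this review, contains no causality guidance that overrides 8.5. The weight is moderate: other safeguards keep the event in view, but the correction is cheap and concerns the primary safety objective.

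**What to change.** In 8.5:

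- *Possibly*: remove the known-pattern condition, so that plausible timing is enough even where another cause might explain the event.
- *Probably* and *Definitely*: make a known pattern supporting evidence rather than a requirement. *Probably* then rests on timing with no reasonable other explanation, and *Definitely* on timing with re-challenge or laboratory confirmation. Changing *Definitely* as well matters, since otherwise a confirmed reaction of a new kind still could not reach it. The grades remain ordered by their other conditions.
- Where the term is kept, say what makes a pattern known and whether the IB is the reference.

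Then read 8.4, 8.5 and 6.4.3 together and reconcile them, so that it is clear how an unexpected AE is graded and whether it counts toward the halt. The halting threshold itself is not part of this point.

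The cost is a few lines in 8.5 and in the case report form guidance. No dose, visit or endpoint changes. The downside is that somewhat more AEs will be graded as related and more may count under 6.4.3, which is the cautious direction in a trial whose first purpose is safety.

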9.2 Other Required Safety Assessments

A clinically significant worsening from Baseline of any abnormal study assessment, such as physical examination, or vital signs, should be considered an AE and recorded accordingly. If possible, a diagnosis for the clinically significant study assessment should be provided by the Investigator (e.g. Urinary tract infection or anemia). In the absence of a diagnosis, the abnormal study assessment itself should be listed as the AE (e.g., bacteria in urine or decreased hemoglobin). An abnormal study assessment is considered clinically significant if the subject has one or more of the following related to the abnormal study assessment:

- 1. Concomitant clinical signs or symptoms.
- 2. Further diagnostic testing or medical/surgical intervention.
- 3. Discontinued from the study.

Repeat testing to determine whether the result is abnormal, in the absence of any of the above criteria, does not necessarily meet clinically significant criteria. The determination of whether the study assessment results are clinically significant must be made by the Investigator.

During the study, AEs will be followed to resolution (return to normal or to the baseline state) or until clinically stable as determined by the Investigator. At the final study visit (Day 14), studyrelated AEs will be followed until resolution or until clinically stable as determined by the Investigator.

10 SPECIAL REQUIREMENTS AND PROCEDURES

10.1 Study Monitoring

The Clinical Monitor and/or the Sponsor representative will arrange to visit and monitor the Investigator's site at regular intervals during the study. The monitoring visits must be conducted according to the applicable International Conference on Harmonization (ICH) and Good Clinical Practice (GCP) guidelines to ensure protocol adherence, quality of data, drug (IP) accountability, compliance with regulatory requirements, and continued adequacy of the investigational site and its facilities. During these visits, source documents to include CRFs, eCRFs and other data related to the study will be reviewed and any discrepancies or omissions will be resolved. The Clinical Monitor will be given access to study relevant source documents (including medical records) for purposes of source data verification. Remote (no visit to the investigative site) monitoring, if performed, will be conducted according to all applicable ICH and GCP guidelines.

During and/or after completion of the study, quality assurance officers named by DermBiont or the regulatory authorities may wish to perform on-site audits. The Investigator is expected to cooperate with any audit and aid and documentation (including source data) as requested.

10.2 Audits and Inspections

The Investigators and clinical sites will permit study related monitoring, audits, IRB/IEC review, and regulatory inspections as requested by FDA, DermBiont or designee, including direct access to source data/documents [i.e., original medical records, laboratory reports, hospital documents, progress reports, signed Informed Consent Forms (ICFs), etc.] in addition to eCRFs.

10.3 Data Quality Control and Quality Assurance

The Investigator is responsible for ensuring the study is conducted according to the protocol, Code of Federal Regulations (CFR), GCP, and applicable regulatory requirements. The responsibilities outlined in these documents along with the identification that a signed informed consent must be obtained prior to a subject participation in the study.

